8.2.2.2. Outcome of safety evaluation

- If no safety concern is observed during the blinded or unblinded data review, the favourable outcome of the safety evaluations will be documented and provided in writing, authorising the Investigator to start vaccination of participants with the subsequent dose as well as enrolment and vaccination of the remaining participants of the next step of the study.
- In case the Investigator becomes aware of one or more holding rules (refer to Section 8.2.2.3), he/she should immediately inform IQVIA of the event (refer to the IQVIA study contact list for contact information).
- If a safety issue is observed during the unblinded data review or if any of the holding rules (e.g. 2a or 2b; Refer to [Table 11](#)) is met, the iSRC Chair (or his/her representative) is responsible for the urgent communication to the GVGH PP, including any rationale for a decision to put the vaccination on hold or not. The GVGH PP will be accountable for notifying all investigators (through IQVIA) of the decision whether to suspend, modify, or continue the conduct of the study on all groups or on selected groups.
- If a safety issue is observed during the blinded data review or a holding rule threshold is met (not known in which study group events occurred), an ad hoc iSRC safety evaluation meeting will be called.

8.2.2.3. Study holding rules

[Table 11](#) shows the holding rules to be implemented for this study. These holding rules have been written under the assumption that the safety data from all participants will be available. If the data from all participants are not available (e.g., in case a participant is lost to follow-up), then the holding rules will be assessed on a pro-rata basis.

Holding rules 1a-d in all steps of the study and holding rule 2c in Step 1a and 1b will be monitored by the Investigator on a continuous basis (threshold ≥ 1 , refer to [Table 11](#)). Meeting any of these holding rules will trigger a hold of study intervention administration irrespective of number of participants enrolled and/or timing of the event.

For holding rules 2a-b in all steps of the study and holding rule 2c in Step 2, the Investigator will inform IQVIA immediately if a threshold is suspected to be met, without pausing administration of the study intervention (threshold $\geq 2-6$, refer to [Table 11](#)). IQVIA will provide a report to the GVGH PP who will then confirm if the threshold has been met and advise whether to pause the study intervention administration.

If the Investigator becomes aware that a holding rule threshold has been met (either directly or via IQVIA), the following communication sequence must be followed:

- The concerned site staff must put study intervention administration on hold.
- The concerned site staff must immediately inform IQVIA CRA and Medical Monitor (contact details will be provided in a separate document) via email and phone communication who will in-turn inform the GVGH Study Responsible Project Physician.

CONFIDENTIAL

205480 (TYPH-PARATYPH A CONJ VI-CRM O2-CRM GVGH-001 (H02_01TP))
Protocol Amendment 2 Final

- All informed site staff will confirm to their local contact that action has been taken providing appropriate documentation to GVGH through the IQVIA CRA and Medical Monitor.
- GSK will further evaluate the case with the iSRC and GSK Global Safety Board and will take the decision to stop or to restart the study intervention administration. GVGH Project Physician will inform the IQVIA project lead of the decision and the rationale for the decision and all site staff will be informed by IQVIA project lead.

Table 11 Study holding rules

Holding rule	Event	Number of participants needed to pause vaccination in the study and trigger further evaluation by the iSRC		
		Step 1a	Step 1b	Step 2
1a	Death or any life-threatening SAE regardless of causality	≥1	≥1	≥1
1b	Any non-life-threatening SAE that cannot be reasonably attributed to a cause other than vaccination as per Investigator or Sponsor assessment	≥1	≥1	≥1
1c	Any withdrawal from the study (by Investigator or participant request) following a Grade 3 AE	≥1	≥1	≥1
1d	Any solicited administration-site event or solicited systemic event leading to hospitalisation, OR Necrosis at the injection site, Each with an event onset within the 7-day post-vaccination period	≥1	≥1	≥1
2a	Any Grade 3 solicited administration-site events (lasting 48h or more as Grade 3), with an event onset within each 7-day post-vaccination period	≥3	≥3	≥6
2b	Any Grade 3 solicited systemic events (lasting 48h or more as Grade 3), with an event onset within each 7-day post-vaccination period	≥2	≥2	≥3
2c	Any Grade 3 unsolicited AE, which can be reasonably attributed to the vaccination as per Investigator or Sponsor assessment, with an event onset within each 7-day post-vaccination period OR Any Grade 3 or above abnormality* in pre-specified haematological or biochemical laboratory parameters collected at 7 days post-vaccination period	≥1**	≥1**	≥2

AE=adverse event, SAE=serious adverse event

*Refer to Section 10.9 for the grading scales to the pre-specified laboratory parameters

**The Investigator should inform IQVIA CRA and Medical Monitor immediately if an event occurs and should follow instruction as applicable to holding rules 1a-1d.

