205480 (TYPH-PARATYPH A CONJ VI-CRM O2-CRM GVGH-001 (H02_01TP))
 Protocol Amendment 2 Final

Type of contact	Screening period	Visit 1 (Priming Vacc)	Sentinel participant safety phone contact	Reminder phone contact 1	Visit 2	Visit 3	Visit 4 (Booster Vacc)	Reminder phone contact 2	Visit 5	Visit 6	Follow-up safety phone contact
Time points	Day -21 to Day -1	Day 1	Day 2	Day 4	Day 8	Day 29	Day 169	Day 172	Day 176	Day 197	Day 337
Recording of solicited events in the participant paper Diary (Days 1-7 post-vaccination) (Section 10.3.8)		○					○				
Recording of unsolicited AEs in the source document (Days 1-28 post-vaccination) (Section 10.3.8)		○	○ ⁷		○		○		○		
Transcription of unsolicited AEs in the eCRF by the Investigator or delegate		●	●		●	●	●		●	●	
Safety surveillance (including vital sign assessment and body temperature measurement) (60 minutes post-vaccination) (Section 10.3.8)		●					●				
Reporting of SAEs (Section 10.3.8)		●	● ⁷		●	●	●		●	●	●
Reporting of SAEs related to study participation or concurrent GSK medication/ vaccine	●	●	● ⁷		●	●	●		●	●	●
Reporting of pregnancies and pregnancy outcomes (Section 10.3.8)		●			●	●	●		●	●	
Recording of AEs/SAEs leading to withdrawal		●			●	●	●		●	●	●
Diary cards											
Distribution of diary cards		○					○				
Phone call for diary card completion reminder (Section 10.3.8)				●				●			

CONFIDENTIAL

 205480 (TYPH-PARATYPH A CONJ VI-CRM O2-CRM GVGH-001 (H02_01TP))
 Protocol Amendment 2 Final

Type of contact	Screening period	Visit 1 (Priming Vacc)	Sentinel participant safety phone contact	Reminder phone contact 1	Visit 2	Visit 3	Visit 4 (Booster Vacc)	Reminder phone contact 2	Visit 5	Visit 6	Follow-up safety phone contact
Time points	Day -21 to Day -1	Day 1	Day 2	Day 4	Day 8	Day 29	Day 169	Day 172	Day 176	Day 197	Day 337
Safety phone call to sentinel participants 1-day post-vaccination to check for any holding rule events or SAEs (Section 8.2.2)			●								
Diary card transcription in the eCRF by Investigator or delegate					●				●		
Return of diary cards					●				●		
Participant study conclusion (Section 4.4)											●

¹A blood pregnancy test will be performed.

²A urine pregnancy test will be performed.

³TYPHIM VI will be the control vaccination at Visit 1 (Day 1)

⁴CCI [REDACTED] will be the control vaccination at Visit 4 (Day 169)

⁵Blood collection will be performed prior to vaccination

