8.2.2.1. Staggered vaccination

Participants will always be vaccinated sequentially. At Visit 1 (Day 1), sentinel participants should receive the first vaccination each 1 day apart and non-sentinel participants should receive it at least 60 minutes apart. At Visit 4 (Day 169), all participants, should receive the second vaccination at least 60 minutes apart. All participants will be closely observed for at least 60 minutes after vaccination.

The Investigator is not permitted to begin dosing study participants in Step 1b or Step 2 until the receipt of favourable written documentation of safety evaluations (iSRC/SRT). Screening procedures may continue, to facilitate the enrolment of remaining participants.

Step 1a:

A “Step 1a low dose without Alum” subgroup comprises 2 study groups (2:1 randomisation [Step 1a low dose without Alum: Step 1a control]) will receive either 2 vaccinations with the candidate low dose Vi-CRM₁₉₇+O:2-CRM₁₉₇ vaccine without Alum

or 1 vaccination with the TYPHIM VI vaccine (as control for the first vaccination) and 1 vaccination with the **CCI** [REDACTED] vaccine (as control for the second vaccination).

First, 6 sentinel participants will receive, on consecutive days, either the low dose of the Vi-CRM₁₉₇+O:2-CRM₁₉₇ or the TYPHIM VI vaccine (2:1 randomisation). Each sentinel participant will be followed up with a safety phone call approximately 1 day after vaccination. If there are any safety concerns, the sentinel participant will be asked to visit the site to assess any potential SAEs or to assess if any holding rules have been met. If no holding rules have been met nor SAEs reported by any of the sentinel participants, 12 additional participants will receive sequentially (at least 60 minutes apart) either the low dose of the Vi-CRM₁₉₇+O:2-CRM₁₉₇ or the TYPHIM VI vaccine, maintaining the 2:1 randomisation.

All available safety data (including laboratory test results) collected until 7 days after first vaccination in Step 1a will be reviewed blindly by the iSRC Chair together with the SRT (Safety evaluation #1; refer to [Table 10](#)). The iSRC Chair and SRT will decide whether an unblinded review by the full iSRC is needed, before initiating the first vaccination in Step 1b (administration of the low dose of the candidate vaccine with Alum or control vaccine to sentinel participants). A positive outcome will also allow the 18 participants in Step 1a to receive further vaccinations as per the SoA.

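### Holding rules 2a/2b: for Grade 3 events the site has not already heard of, no scheduled contact asks before the diary returns at 7–10 days; a question at the Day 4 and Day 172 calls would bring part of the count forward

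*Protocol*

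**What the plan says.** Protocol Section 8.2.2.3, Table 11, sets rule 2b on "Any Grade 3 solicited systemic events (lasting 48h or more as Grade 3", with onset in the 7 days after a dose. The threshold is 2 participants in Step 1a, 2 in Step 1b and 3 in Step 2. Rule 2a is the same for administration-site events, with thresholds of 3, 3 and 6.

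Solicited events are captured in a paper diary (Section 10.3.8). The Schedule of Activities (Section 1.3, Table 1) places "Diary card transcription in the eCRF by Investigator or delegate" at Visit 2 and Visit 5, which Table 2 allows 7 to 10 days after the dose. Two scheduled contacts come earlier:

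- Day 2, sentinels after dose 1 only: "Safety phone call to sentinel participants 1-day post-vaccination to check for any holding rule events or SAEs".
- Day 4 and Day 172, all participants: "Phone call for diary card completion reminder". No adverse-event, SAE or solicited-event row is marked in these columns. Table 2 lets the second call fall 1 to 3 days after Visit 4.

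Section 8.2.2.1 starts the remaining participants of a step "If no holding rules have been met nor SAEs reported by any of the sentinel participants". After that, "non-sentinel participants should receive it at least 60 minutes apart". No daily maximum is stated.

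If a 2a/2b threshold is only suspected, "the Investigator will inform IQVIA immediately if a threshold is suspected to be met, without pausing administration of the study intervention". Once the Investigator knows that a threshold is met, Sections 8.2.2 and 8.2.2.3 require dosing to be put on hold.

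**The concern.** A rule meant to pause dosing is only as prompt as the information behind it. The Day 2 call is the scheduled check before non-sentinel dosing, but it comes before a 48 h duration can have elapsed. The next scheduled contact is late enough but carries no safety question. A participant with two days of Grade 3 fatigue or myalgia who does not ring the site therefore first becomes visible when the diary is handed in.

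At stake is the number exposed within a step, chiefly in Step 2, where 55 participants follow 5 sentinels at the first use of the full dose. The O:2 component has no earlier human safety data (Sections 2.3 and 4.3). After dose 2 there is no sentinel spacing and no 1-day call, so the reminder is the only scheduled contact before the diary.

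**Working it through.** **1. What each contact can establish.** A contact t hours after the dose can confirm a 48 h event only if onset was at or before t − 48 h. The study days reproduce the planned intervals in Table 2: 8 − 1 = 7 days and 176 − 169 = 7 days.

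| Contact | t | Latest onset that can show 48 h | Asks about 2a/2b? |
|---|---|---|---|
| Day 2, sentinels | 24 h | none (24 − 48 < 0) | yes |
| Day 4, all | 72 h | 24 h | no |
| Reminder call 2 at 1 / 2 / 3 days | 24 / 48 / 72 h | none / 0 h / 24 h | no |
| Visit 2 or 5, earliest | 168 h | 120 h | yes, from the diary |

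**2. Sentinels.** Take one sentinel per calendar day and non-sentinel dosing opening on the day of the last sentinel's call. Day 4 calls are then due for 4 of 6 sentinels (Steps 1a, 1b) or 3 of 5 (Step 2), and no diaries are due. With 4 active sentinels and a 15% event rate, sentinels alone reach rule 2b with probability P(≥2 of 4) = 11.0% in Steps 1a/1b and P(≥3 of 4) = 1.2% in Step 2. Most of the issue therefore lies with non-sentinels.

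**3. Number dosed in Step 2 before rule 2b is known to be met.** The documents give no dosing pace, event rate or onset distribution, so these inputs are assumptions. Simulation, 6,000 runs per setting:

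- 5 sentinels at one per day (4 active), then 55 others (44 active).
- Event rate p in active participants, none in controls.
- Diary read at 7 days, the earliest allowed; call at 3 days; weekend reports move to Monday.
- A share f of events is known at the call, the rest from the diary.
- No spontaneous reports, an immediate hold and no repeat calls.
- Means are over runs in which the threshold is reached.

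| Setting | Diary only | With call, f = 50% / 100% | Fewer dosed |
|---|---|---|---|
| p = 15%, 4 per day, 5-day week | 44.8 | 39.9 / 35.4 | 4.9 / 9.4 |
| p = 10%, same | 50.2 | 46.1 / 42.0 | 4.1 / 8.2 |
| p = 5%, same | 54.8 | 52.1 / 48.7 | 2.7 / 6.1 |
| p = 15%, 2 per day | 34.6 | 32.0 / 29.6 | 2.6 / 5.0 |
| p = 15%, 8 per day | 58.6 | 52.9 / 47.9 | 5.7 / 10.7 |
| p = 15%, 4 per day, 7-day week | 51.2 | 44.3 / 37.5 | 6.9 / 13.7 |

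Rule 2a gains less: 56.6 against 54.0 / 50.5 in the setting of the first row. In Steps 1a/1b, rule 2b at 2 per day gives 17.1 against 15.9 / 14.7 of 18.

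**4. Less favourable assumptions**, each applied to the first row:

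- Confirmation delay before the hold: about 3–6.5 fewer with 1 calendar day and 2–4 with 2; less if counted in working days.
- Half of events reported spontaneously by day 3: about 2–4.5.
- Onset uniform over 7 days (f = 1/7): about 1.4.

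**5. Chance that the threshold is reached.** With 48 active participants, P(X ≥ 3) = 1 − Σ(k = 0 to 2) C(48,k) p^k (1 − p)^(48−k). At p = 5% this is 1 − (0.0853 + 0.2154 + 0.2664) = 43%. At 1%, 2.5%, 10% and 15% it is 1%, 12%, 87% and 98%. The same binomial model reproduces Table 14 (for example 1 − 0.90^24 = 92.0%). Averaged over all runs at p = 5%, the saving is 0.43 × 2.7 to 0.43 × 6.1, or about 1.2 to 2.6 of 60. Rule 2a (6 or more) is reached in 75% of runs at p = 15%.

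**The case against.** The plan has more protection than its call schedule suggests.

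- **Sentinels.** A Grade 3 event reported at the Day 2 call must be followed at later contacts (Section 10.3.8.2), and Day 4 is one. If there is a concern, "the sentinel participant will be asked to visit the site to assess any potential SAEs or to assess if any holding rules" have been met. This stands, and it covers the early onsets that a Day 4 question could confirm. The point is therefore limited to events not already known.
- **Participant contact.** Section 10.3.4 tells participants to contact the site about medically attended events and about any others that concern them. Section 10.3.8 adds symptoms they perceive as serious. Many two-day Grade 3 events would come in this way, but not reliably all of them.
- **Suspected thresholds do not pause dosing.** An answer given by telephone is most naturally a suspected count, so confirmation time cuts the gain. This stands. A reader might infer that dosing continues even after a threshold is met; the documents do not support that, because a known threshold requires a hold, and the single site sees every case.
- **Rates.** 15% is high for Grade 3 systemic events lasting 48 h. Table 14 also considers 1% and 2.5%, where rule 2b is rarely reached.
- **Deliberate design.** Section 8.2.2.3 reserves continuous monitoring for rules 1a–1d and, in Steps 1a/1b, rule 2c. The safety review team also monitors blinded data throughout. Even so, the rule expects immediate notice of a suspected 2a/2b threshold, which earlier information would serve.
- **Leading questions.** Section 8.3.2 prefers open, non-leading questioning. Suitable wording meets this.
- **Unseen manuals.** The Study Procedures Manual may already script the call. If so, the change only records existing practice.

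**Conclusion.** The point holds in a limited form. For Grade 3 solicited events the site does not already know about, mainly in non-sentinels and in all participants after dose 2, no scheduled contact asks about rules 2a/2b before the diary returns.

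A reader might go further and infer that the two rules cannot operate before the diary, or that the sentinel stage or escalation is unprotected. The documents do not support this. Sentinel events have a follow-up route, participants can report at any time, rules 1a–1d act on a single case, and data to 7 days after the first dose are reviewed before the next step opens. No endpoint is affected.

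The first-row saving of 5–9 of 60 is an upper value for its setting, because it assumes no spontaneous reports and an immediate hold. Over all paces, rates of 5–15% and both working weeks, the corresponding figures run from about 1 to 14. All are conditional on rule 2b being reached. Repeat calls, which would add a little, are not modelled, and dose 2 is not quantified. The schedule facts are firm; the size is uncertain. This is an optional to recommended safety improvement.

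**What to change.** In the Schedule of Activities and Section 8.2.2.3:

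1. At the Day 4 call and at reminder call 2, ask an open, non-leading question: whether any symptom since vaccination has prevented normal activity, or there has been fever of 39.0°C or more or redness or swelling over 100 mm, and since when. Record the answer.
2. If a Grade 3 event has lasted under 48 h, call that participant again when 48 h would be reached. This also allows the 1–3 day window for reminder call 2 to stay.
3. State that such events count towards a suspected 2a/2b threshold under the existing report-then-confirm route and are reconciled with the diary at Visit 2 or 5. The diary stays the only source for the primary endpoint.

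Thresholds and the hold for a known threshold do not change. The cost is slightly longer calls, occasional repeat calls and some reconciliation, with no added visit. The gain is partial: at 3 days only onsets within about 24 h of the dose can show 48 h.

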8.3. AEs, SAEs, and other safety reporting

8.3.1. Time period and frequency for collecting AE, SAE, and other safety information

Table 12 Timeframes for collecting and reporting of safety information

	SCR* D-21 to D-1	VAC 1 D1	D8	D29	VAC 2 D169	D176	D197	SFU D337
Administration-site and systemic solicited events		D1 to D7			D169 to D175			
Unsolicited AEs**		D1 to D28			D169 to D196			
AEs/SAEs leading to withdrawal from the study					D1 to D337			
SAEs**					D1 to D337			
SAEs related to the study intervention					D1 to D337			
SAEs related to study participation or concurrent GSK medication/ vaccine***					D-21 to D337			
Pregnancy					D1 to D197			
Any other event of interest for the study					D1 to D197			

*Consent obtained

**Unsolicited AEs/SAEs due to COVID-19 will be recorded according to the WHO case definition [WHO, 2022].

*** Any SAEs assessed as related to study participation (e.g., protocol-mandated procedures, invasive tests, or change in existing therapy) or related to a GSK product will be recorded from the time a participant consents to participate in the study.

D=Day; SFU=safety follow-up; SCR=Screening; VAC=Vaccination

The Investigator or designee will record and immediately report all SAEs in enrolled participants to the Sponsor or designee via the Expedited AE Reporting Form. Reporting should, under no circumstances, occur later than 24 hours after the Investigator becomes aware of an SAE, as indicated in Section 10.3.10. The Investigator will submit any updated SAE data to the Sponsor or designee within 24 hours of it being available. SAEs

related to study participation or to a concurrent GSK medication/vaccine will be collected from the time consent is obtained until the participant is discharged from the study.

During the extended safety follow-up period (Day 197 to Day 337), participants will be encouraged to inform the Investigator in a timely manner if they have any event meeting the description of an SAE. Any SAE reported during this period will qualify for expedited reporting according to Section 10.3.10. Any SAEs discovered retrospectively during the safety phone call on Day 337 will also be reported accordingly.

A post-study AE/SAE is defined as any event that occurs outside of the AE/SAE reporting periods defined in Table 12. Investigators are not obligated to actively seek AEs or SAEs from former study participants. However, if the Investigator learns of any SAE, including a death, at any time after a participant has been discharged from the study, and he/she considers the event to be reasonably related to the study intervention, the Investigator will promptly notify the study contact for reporting SAEs mentioned in the IQVIA study contact list.

8.3.2. Method of detecting AEs and SAEs, pregnancies, and other events

Detection and recording of AE/SAE/pregnancies are detailed in Section 10.3.8.

Assessment of AE/SAE intensity, causality and outcome are described in Section 10.3.9.

Open-ended and non-leading verbal questioning of participants is the preferred method of acquiring information related to an AE/SAE/pregnancy.

8.3.2.1. Clinically significant abnormal laboratory findings

The Investigator must review the laboratory report, document that he/she did so, and record any clinically relevant changes occurring during the study in the AE section of the eCRF. Clinically significant abnormal laboratory findings are those which are not associated with an underlying disease, unless judged by the Investigator to be more severe than expected for the participant's condition.

- All laboratory tests with clinically significant abnormal values reported during the study should be repeated until the values return to normal/baseline, or until they are no longer considered significantly abnormal by the Investigator. Refer to Section 10.3.6 for more information on clinically abnormal laboratory assessments that qualify as an AE or SAE.
- In case abnormal values are not considered clinically significant by the Investigator, additional evaluations could be requested by the GVGH PP.
- If abnormal values do not return to normal/baseline after an interval judged reasonable by the Investigator, the aetiology of the abnormal value should be identified, and the Sponsor notified.

